6.3. Randomisation

Following completion of baseline information collection, a member of the research team will randomise the participant to one of the two treatment arms: physicist consultation or standard of care.

Patients will be randomised in order to minimise systematic bias, using a secure web-based system Sealed Envelope (https://www.sealedenvelope.com/simple- randomiser/v1/trials/rapport), certified as meeting ISO/IEC 27001 standards and the NHS England Data Security and Protection Toolkit.

Participants will be allocated to intervention group or to the control group in a 1:1 ratio. Randomisation will be stratified by gender. This is a surrogate for treatment site: the most common radiotherapy treatment sites (particularly at RWRC) are breast and prostate cancer. However, to ensure approximately equal distribution of treatment sites in each arm and avoid problems of low numbers of less common treatment sites, gender has been chosen has the stratification criteria. It is acknowledged that with the low sample size required in this study, distribution is likely still to be unequal but there is little evidence that the primary outcome varies by gender.

Upon randomisation, each participant will be assigned a unique Trial Number which will be used as the principal identifier on trial data collection forms and questionnaires. The research team member will disclose the allocation to the participant and will ensure the allocation is followed as described below.

6.4. **Provision of Treatment**

Following allocation, the participant will be informed of which trial arm they have been randomised to. Where required, the consultation will be booked by the PI or delegate and the patient informed what time this will be (as it will not be on their routine appointment list given at the CT appointment). If possible, a reminder will be sent via the DoctorDoctor service.

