8. STATISTICS AND DATA ANALYSIS

8.1. Sample size calculation

Advice on the sample size calculation has been sought from [name], Principal academic in healthcare statistics at Bournemouth University.

The study is powered to detect a 10-point difference in patient-reported anxiety on the STAI. There is evidence that this is the minimally important difference (MID)^{18,42,66}. An estimate of standard deviation was made from work by Burmeister⁴² and Atwood³⁶ in similar radiotherapy populations, both studies used the STAI to measure patient anxiety. Atwood found standard deviations ranging from 10.2-15.6, whilst Burmeister found a lower standard deviation of 8.1. A standard deviation of 13 has been chosen to represent an average within the range of observed values from Atwood.

Based on an unpaired t-test with two groups of equal size, assuming 80% power, a twosided 0.05 significance level, a standard deviation of 13 and a mean difference of 10 points in patient-reported anxiety, a total sample size of 54 (27 in each group) is required. The study will over-recruit by 10% to allow for non-responders, missing data, or attrition (dropout). Therefore, the study will aim to recruit 60 patients in total (30 in each group) over a 1year recruitment period. This gives a similar sample size to the work of Atwood, and a sample size 1.5 times larger than Burmeister.

This sample size is also in the region of that calculated by an independent method (using the varying-slope varying-intercept model). Whilst this doesn't consider the repeated timepoints as independent, it represents a worst-case scenario. The details of this calculation are in Appendix 1, but the calculated sample size is 76 (although this doesn't account for attrition), slightly larger than the sample size calculated but of the same magnitude.

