8.2.1. Baseline Descriptives

Baseline descriptive data on demographics (gender, age, marital status, employment status, education level), health literacy) will be presented overall and for both groups separately. This will help to see whether the 2 groups were comparable at baseline.

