8.2.2. Primary outcome

The primary outcome is the Spielberg state-trait anxiety index (STAI). Questionnaires that were not completed in the required timeframes will be treated as missing data:

- Baseline within 1 week of CT appointment
- Start of treatment on day of treatment
- End of treatment on day of treatment

Anxiety scores will be compared at each time point between the two groups for a statistically significant difference. The 2nd and 3rd timepoints will use baseline-corrected anxiety scores. Some additional analyses (including sensitivity analyses) on the primary outcome will also be conducted:

- a. The effectiveness of the intervention may vary across different subgroups of patients (e.g. age, education level). Therefore, supplementary statistical analyses are proposed in which it is tested if there is a statistical interaction between socio-demographic data and the primary outcome. This will include health literacy level measured at baseline.
- b. Any baseline variables that appear, by chance, to differ between the groups will be added in as covariates.
- c. Whether or not the patient has had previous radiotherapy will be added as a covariate.
- d. Longitudinal analysis of anxiety scores at all three time points to assess variation across treatment
- e. Proportions of high and low anxiety scores in each group at each time point.

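### Section 8.2.2 item b picks the covariates of an additional adjusted analysis by apparent baseline imbalance; a short list fixed in advance on expected prognosis should replace it

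*Protocol*

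**What the plan says.** Section 8.2.2 compares STAI between arms at each timepoint, and for the two follow-up timepoints "The 2nd and 3rd timepoints will use baseline-corrected anxiety scores". It then adds: "Some additional analyses (including sensitivity analyses) on the primary outcome will also be conducted". Item b of that list reads: "Any baseline variables that appear, by chance, to differ between the groups will be added in as covariates". No candidate list, threshold or prognostic criterion goes with it. Item c fixes one covariate in advance: "Whether or not the patient has had previous radiotherapy will be added as a covariate".

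The table that feeds item b is described in section 8.2.1: "Baseline descriptive data on demographics (gender, age, marital status, employment status, education level), health literacy) will be presented overall and for both groups separately". Its purpose is also given: "This will help to see whether the 2 groups were comparable at baseline". Section 6.3 states: "Randomisation will be stratified by gender". Gender is not named as a covariate in section 8.2.2.

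**The concern.** In a randomised trial any baseline difference between arms arises by chance, so apparent imbalance says nothing about whether a variable should be in the model. What matters is how strongly it predicts anxiety. Item b therefore admits variables that look imbalanced but may not be prognostic (marital or employment status, for example) and leaves out prognostic ones that happen to look balanced. Gender, held near balance by stratification, will tend to be left out.

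Whether a variable appears to differ is a judgement made with the arms shown separately. Section 3.2 promises pseudonymised analysis, which is not analysis blind to arm. The fitted model then varies from one realisation of the trial to the next and with a threshold nobody has written down. An additional analysis is meant to test how firm the main result is, and one whose model depends on the draw does that poorly.

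**Working it through.** **1. The plan's own figure.** Section 8.1 gives the inputs: "assuming 80% power, a twosided 0.05 significance level, a standard deviation of 13 and a mean difference of 10 points".

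- n per arm = 2(1.960 + 0.842)² × (13/10)² = 2 × 7.85 × 1.69 = 26.5, so 27 per arm and 54 in total. 54/0.9 = 60. The plan's figures reproduce.
- Power at 27 per arm is 80.7% by normal approximation and 79.2% by exact t.

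**2. How often item b would act.** With k independent candidates, P(at least one flagged) = 1 − (1 − α)^k.

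- Six variables (those in the baseline table): 1 − 0.95⁶ = 26% at p<0.05 and 1 − 0.90⁶ = 47% at p<0.10. In simulation, 93% at a standardised mean difference (SMD) above 0.25.
- Thirteen variables (the items collected under section 6.2.2, leaving out contact details, gender and previous radiotherapy): 1 − 0.95¹³ = 49% and 1 − 0.90¹³ = 75%.

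Independence and the cut-offs are assumptions. Counting stratified gender among the six slightly overstates the first line.

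**3. Size and power of the rule.** Simulation with 27 per arm, outcome SD 13, 10-point effect, and independent normal covariates jointly explaining R² of the outcome (20,000 null and 8,000 alternative trials per setting). Ranges run over three readings of item b: p<0.05, p<0.10 and |SMD|>0.25.

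| Covariates, R² | Size, item b | Power, item b | Power, all fixed in advance |
|---|---|---|---|
| 1, 0.25 | 3.7-4.3% | 79-84% | 88-89% |
| 1, 0.50 | 2.8-3.5% | 81-89% | 97-98% |
| 6, 0.25 | 3.8-4.2% | 78-80% | 84-85% |
| 6, 0.50 | 2.3-3.9% | 81-87% | 95-96% |
| 6, 0.10 | 4.6-4.8% | 78-79% | 78-79% |
| 6, 0 | about 5% | 75-77% | 73-74% |

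Fixed adjustment held its size near 5% throughout. The rule is conservative because it removes false positives in trials where a prognostic covariate is imbalanced, yet tests the balanced-looking trials against the full unadjusted residual variance.

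**4. Where the power gap comes from.** A second simulation uses a change-score outcome, single-timepoint SD 13, 54 patients, baseline STAI plus six other covariates (standardised slope 0.2 each), the p<0.10 rule and 4,000 trials per setting. Power at baseline correlation r:

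| Analysis | r=0.3 | r=0.5 | r=0.7 |
|---|---|---|---|
| Change score, unadjusted | 66% | 80% | 94% |
| Item b | 67% | 82% | 96% |
| Baseline STAI always in | 83% | 90% | 97% |
| Baseline STAI always in, item b for the other six | 83% | 90% | 98% |

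Item b costs nothing against the unadjusted change score. Once baseline STAI is in, it costs nothing against the fixed model either. With six non-prognostic covariates (slope 0) the cost on top of baseline STAI is about 1 to 3 points (80/87/96% against 83/89/97%).

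Algebra agrees. If the change score has SD 13 and the variances at the two timepoints are equal, the residual SD after adjusting for baseline is 13 × √((1 + r)/2): 10.5, 11.3 and 12.0 at r = 0.3, 0.5 and 0.7. Exact-t power is then about 93%, 89% and 85%. Simulation, which allows for chance baseline imbalance, gives 84-93%, against 78-80% for the unadjusted change score and 78-80% for item b.

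**5. How often the verdict moves.** At the planned effect, item b and the unadjusted test disagree at 0.05 in 3-11% of trials with single-timepoint SD 13, and in about 6-9% with change-score SD 13.

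**The case against.** The strongest reply is that item b is harmless. It stands under additional and sensitivity analyses, so the main baseline-corrected comparison, its 5% size and the sample size do not depend on it. That is correct.

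Three stronger readings are tempting, and the protocol does not support them:

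- **Inflated type I error.** The departure from 5% is downwards. Choosing the threshold after seeing results could do other damage, but that was not simulated and is not quantified here.
- **A primary result that can be pushed across 0.05.** Only a supplementary result beside it can move.
- **Lost power caused by item b.** Step 4 shows that the gap to fixed adjustment comes almost entirely from baseline STAI, which is a separate question about how baseline is corrected for.

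It can also be said that the statistical analysis plan, which section 8.2 requires before any analysis, could set a candidate list and a numerical criterion. That would remove the discretion. It would not remove selection by imbalance, which the protocol itself prescribes, and a plan with fixed covariates in its place would contradict the protocol.

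Finally, the size effect needs prognostic covariates. At R² = 0.10 it nearly vanishes, and at R² = 0 fixing all six loses power. This stands, and it argues for a short list, not for adjusting for everything.

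**Conclusion.** The point holds as a flaw in a supplementary analysis. Item b chooses its model from the data, by an unstated threshold, on a criterion unrelated to prognosis. With prognostic covariates the test runs at about 2.5% to 4.3% instead of 5% (2.3% in the most extreme setting tried), and its verdict departs from the unadjusted one in up to roughly 10% of trials at the planned effect. With non-prognostic covariates its size stays at 5%. The number of covariates, their strength, their independence and the thresholds are all assumptions, because the protocol states none. It merits a wording change and does not put the main comparison in doubt.

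**What to change.** Delete item b and merge item c into one sentence, for example: *An adjusted analysis of STAI at each follow-up timepoint will include baseline STAI, gender and previous radiotherapy as covariates, whatever their observed balance. Other baseline differences will be described, and no covariate will be added because of an observed difference.* The statistical analysis plan should carry the same line.

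The cost is a short protocol amendment. All three variables are already collected at baseline (section 6.2.2), and three model terms are affordable with about 54 patients. Baseline STAI brings most of the power gain. An unexpected imbalance in an unlisted variable will be reported but not adjusted for. The subgroup and interaction analyses in item a are untouched.

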4.3.3. Comparison at each visit

Longitudinal analysis of patient-reported state anxiety at each timepoint, and comparison of the number of "high" and "low" anxiety patients in each arm at each timepoint (determined using a threshold value of 40 for the STAI).

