8.2.4. Exploratory outcomes

The exploratory outcomes will not be tested for statistical significance. Correlation with group anxiety scores will be tested against:

- a. Technical satisfaction
- b. Patient information needs
- c. Treatment adherence (appointment attendance and bladder filling)

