12. APPENDICIES

12.1. Appendix 1: Independent Sample Size Calculation

The following is provided by [name].

Similar to the currently proposed study, [42] also describes itself as a two-group repeated measures design with patients modelled as random effects and patient visits as the repeats. While the model is not explicitly stated we can postulate a similar model here that captures the current scenario and explicate in more detail its different components and the assumptions we will make. With a repeated measures-type design we can choose to fit the data using a varying-slope varying-intercept model i.e. $y_{i,t} \sim N(\alpha_i + \beta_i t, \sigma_v^2)$ where j is patient and t indexes time while the variance term reflects a combination of error terms deriving from measurement error, variation in the STAI and departures for each patients' repeated data from the assumed linear model. We can further assume that the anxiety treatment will affect the slope but not the intercept (since at the baselinfiguree time zero there is no treatment). From [36], we can compute that the slope for controls is -.2 and the slope for the intervention group is -4.85. We can also derive the mean of the control group (at baseline) as 36.3 from the same paper. To complete the model we need three further standard deviations, (i) the residual standard deviation (taken as the larger of the two deviations computed from the Altman paper – 2.57) (ii) the intercept standard deviation (computed from Fig4 in Altman) as 11.31. For (iii) the time-by-treatment effect slope standard deviation, neither paper reports these values and so the main assumption for these power calculations are that this standard deviation will be at best equal to the residual standard deviation and at worst equal to the baseline mean standard deviation.

Study design: We assume that N-patients will be randomly assigned into two treatment groups (intervention/control), with N/2 receiving the anxiety intervention and N/2 receiving no such intervention. We further assume that the patients will have repeated equi-spaced visits=3 where the first visit is taken as baseline. We need to determine the N required for 80% power, if the true treatment effect is -4.65, as assumed above.

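### The exploratory high/low anxiety comparison uses crude proportions above a cut of 40, so a chance baseline gap carries into it; adjusting for the baseline STAI already collected would largely remove this

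*Protocol*

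**What the plan says.** Section 8.2.2 compares anxiety scores between the groups at each time point and adds: "The 2nd and 3rd timepoints will use baseline-corrected anxiety scores". It then lists additional analyses of the primary outcome. Item e reads in full: "Proportions of high and low anxiety scores in each group at each time point". No baseline adjustment is attached to it.

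Section 4.3.3, under exploratory outcome measures, describes the same analysis as a count of patients falling on either side of the threshold. Its wording is: "anxiety patients in each arm at each timepoint (determined using a threshold value of 40 for the STAI". Table 1 also places it among the exploratory objectives, at recruitment and before first and last treatment.

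Three other statements bear on it:

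- Item b of section 8.2.2: "Any baseline variables that appear, by chance, to differ between the groups will be added in as covariates".
- Section 8.2.4: "The exploratory outcomes will not be tested for statistical significance". The list that follows does not name the high/low comparison.
- Section 6.3: randomisation is stratified by gender only.

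**The concern.** The protocol does not call the proportions crude, but no other reading works. Section 4.1 gives the score a range of 20 to 80. A change from baseline does not lie on that range, so a cut of 40 can be applied only to the uncorrected score. The baseline correction promised for the continuous score therefore cannot carry over to item e.

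The Background section notes that a US trial of physicist consultations was criticised for using average scores at each time point rather than comparing patients with their own baseline, and regards such criticisms as minor. The protocol meets the point for the mean score but leaves it open for the threshold.

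The stake is modest but real. Section 7.2 links a score of 40 to clinically significant symptoms, so the share of patients above it is an easily quoted result. If one arm happens to start with more high scorers, part of that gap will reappear at first treatment and may look like a consultation effect or hide one.

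**Working it through.** **1. The plan's own figure.** Section 8.1 uses "a standard deviation of 13 and a mean difference of 10 points in patient-reported anxiety", "assuming 80% power, a twosided 0.05 significance level". By the normal approximation, n per arm = 2 × (1.960 + 0.842)² × 13² / 10² = 26.5, so 27 per arm and 54 in total. With 10% attrition, 54 / 0.9 = 60. Both figures reproduce. (The exact t-test gives 28 per arm, and power at 27 is 79.2%. This makes no difference here.) The protocol gives no figure for the high/low proportions.

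**2. Proportion high at baseline.** Appendix 1 states: "We can also derive the mean of the control group (at baseline) as 36.3 from the same paper". It gives an intercept SD of 11.31. Assuming normality:

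- Mean 36.3, SD 11.31: P(score ≥ 40) = 1 − Φ((40 − 36.3) / 11.31) = 0.372, about 10 of 27 per arm.
- Mean 36.3, SD 13 (section 8.1): 1 − Φ(3.7 / 13) = 0.388.
- Mean 40: 0.50. This is included because section 7.2 expects higher anxiety than in a normal population and cites radiotherapy patients most of whom scored 40 or above.

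**3. How often the arms start apart.** The standard error of the baseline difference is √(2p(1 − p) / 27), which is 0.132 at p = 0.372 and 0.136 at p = 0.50. A gap of 15 points or more means at least 5 of 27 patients (18.5 points), because 4 of 27 is 14.8 points. From two independent binomials, the probability of such a gap is 0.20 at p = 0.372, 0.21 at p = 0.388 and 0.22 at p = 0.50. When it occurs, it averages 23 points.

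**4. How much carries over with no effect.** For a two-valued status with the same marginal proportion at both visits, the expected follow-up difference is φ × the baseline difference. Here φ = (P(high at both visits) − p²) / (p(1 − p)). The visit correlation is not in the protocol, so 0.3 to 0.7 is assumed.

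| Correlation | φ (mean 36.3, SD 11.31) | φ × 23.0 points | φ (mean 40) | φ × 23.3 points |
|---|---|---|---|---|
| 0.3 | 0.189 | 4.4 | 0.194 | 4.5 |
| 0.5 | 0.327 | 7.5 | 0.333 | 7.8 |
| 0.7 | 0.488 | 11.2 | 0.494 | 11.5 |

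Simulation with 40,000 trials per setting agrees. The carry-over is about 4 to 11 points and hardly depends on the baseline mean.

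*Example* (36.3, 11.31, correlation 0.5): 57.7% of high patients stay high and 25.0% of low patients become high. If the arms start with 13 and 8 high, the expected counts at follow-up are 13 × 0.577 + 14 × 0.250 = 11.0 and 8 × 0.577 + 19 × 0.250 = 9.4. That is a difference of about 6 points from the baseline split alone.

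**5. Over all randomisations.** With no effect, the crude two-proportion test rejects in 4 to 5% of simulated trials and the mean difference is zero.

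**6. With adjustment.** The simulation used a linear model of high status on arm and continuous baseline STAI. In trials with a gap of 15 points or more, the carry-over falls to about 0 to 1 point (at most 1.5 over the settings). With a true 10-point effect, 27 per arm, and taking a 5% two-sided test only as a yardstick for precision:

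| Baseline mean, SD | Crude power | Adjusted power at correlation 0.3 / 0.5 / 0.7 |
|---|---|---|
| 36.3, 11.31 | 65% | 64% / 67% / 74% |
| 36.3, 13 | 55% | 54% / 58% / 65% |
| 40, 13 | 58% | 60% / 64% / 72% |

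At correlation 0.3 adjustment makes little difference; above that it gains precision.

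**7. Masking.** With SD 13, a true 10-point effect gives a crude difference of 24 to 28 points on average. Given a baseline gap of at least 20 points (about 10 to 13% of trials), that becomes 15 to 24 points if the consultation arm starts higher and 28 to 39 points if it starts lower.

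**The case against.** **Exploratory and apparently untested.** Section 4.3.3 and Table 1 class this as exploratory, and section 8.2.4 says such outcomes are not tested. That stands, and arguments from false-positive rates carry little weight. But section 8.2.2 also lists item e among additional analyses of the primary outcome, so its status is not wholly clear. An untested estimate is still read as an effect.

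**Baseline is not ignored.** A reader might infer that the plan overlooks baseline status. It does not: the proportions are given at all three time points, so a gap would be visible, and item b provides a covariate rule for chance imbalance. Seeing a gap does not take it out of the follow-up difference, however. Item b depends on the observed data and is not linked to item e.

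**Most patients starting low.** The 36.3 invites this inference, along with the idea that most patients cannot move down. The figure is a simulation input taken from another trial's control group, and section 7.2 points the other way. Patients who start low are also informative, since they can become high. The carry-over does not depend on the point.

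**Valid by randomisation.** A reader might infer an inflated error rate. Step 5 shows none; what remains is bias conditional on the observed baseline gap, and lost precision.

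**Left to the analysis plan.** Section 8.2 promises one, and the model could be set there. That limits the point to a minor improvement.

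**Conclusion.** The point holds as a minor improvement to an exploratory analysis. The high/low comparison is crude while the continuous score is baseline-corrected. In about one trial in five of this size, a baseline gap of 15 points or more would carry about 4 to 11 points into the follow-up difference with no consultation effect. The frequency rests on 27 evaluable patients per arm and a baseline proportion high of 37 to 50%. The carry-over rests also on normal scores and an assumed visit correlation of 0.3 to 0.7, of which the protocol gives neither. The baseline-corrected primary comparison is not touched.

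**What to change.** In sections 4.3.3 and 8.2.2 item e:

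- Estimate the arm difference in high status at first and at last treatment with a risk-difference or logistic model adjusted for continuous baseline STAI. If logistic, convert the result to a risk difference by averaging predictions, so that it reads on the same scale as the proportions.
- Show the follow-up proportions by arm within baseline high and baseline low patients, as description only. At a baseline proportion of 0.372 the high group would have about 10 patients per arm.
- State that the estimate is exploratory, so that section 8.2.2 agrees with sections 4.3.3 and 8.2.4.
- State whether a score of exactly 40 counts as high. Section 4.3.3 leaves this open; the cohort cited in section 7.2 is described by scores of 40 or above.

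The cost is wording in two sections, one model and one table. Baseline STAI is already collected under section 6.2.2.
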